9.3.3 Covariate Assessment

The following sociodemographic characteristics will be collected and used to describe the respondent sample:

- Country
- PAC provided in a language respondent is fluent or proficient at (yes/no)
- Age group (<65 years; >65 years)
- Sex (male/female)
- Educational level (categories vary by country)
- Respondent type (patient/caregiver)
- Respondent health literacy (BHLS ≤ 9 points; BHLS > 9 points (Willens et al. 2013))
- Number of previous OBI administrations

9.3.4 Validity and Reliability

Qualitative techniques will be used to ensure that the respondent questionnaire is readable, understandable and easy-to-use.

The questionnaire will be developed in English language and conceptually reviewed by 5 patients who have received Neulasta (not through the OBI) or, if applicable, their caregivers in the UK. The questionnaire will be subsequently translated and linguistically validated with 3 patients/caregivers in each of the participating countries. Patients who have received the OBI or caregivers taking care of these patients will not be used to validate the questionnaire so that the recruitment for the study is not affected.

During the linguistic validation interviews, trained interviewers will ask participants to complete the questionnaire while 'thinking aloud' and to describe their thinking and thought processes as they answer each question, each section, and the questionnaire overall. The results will be used to optimize instructions, guidance, wording, response choices, as well as language.

A master version of the questionnaire will be generated following linguistic validation in the participating countries.

The eCRF will be developed and administered in English and we do not anticipate the need of validating it.

Date: 10 April 2019 Page 24 of 61

9.4 Data Sources

Data for this study will be collected through a questionnaire developed for the primary person responsible for monitoring the OBI after application (ie, patients or, if appropriate, their caregivers). Responses will be collected either by **paper** or online.

The questionnaire has been developed following standard questionnaire principles (Bowling, 2014). It will mainly include multiple choice questions with limited free text fields.

In addition, an eCRF for the HCP will be used to collect descriptive information about the HCP and site, information about the time and date of OBI administration, and of events related to medication errors.

9.5 Study Size

This study aims to include approximately 80 respondents, however, the final sample size will ultimately depend on the uptake of the OBI in participating countries and willingness of respondents to participate. Expected OBI use in Europe is <10,000 patients per year, therefore, a sample size of 80 respondents is considered feasible.

Table 2 gives the 95% confidence interval half-width around the proportion of respondents with correct answers to the questions around awareness and behavioural intent for a given sample size of questionnaire respondents.

Table 2. Half-width of 95% Confidence Intervals for Different Proportions of Correct Answers to Questions by Size of Questionnaire Respondents

Sample Size	Proportion	Half-width 95% CI
60	0.5	0.13
60	0.6	0.12
60	0.7	0.12
60	0.8	0.10
60	0.9	0.08
80	0.5	0.11
80	0.6	0.11
80	0.7	0.10
80	0.8	0.09
80	0.9	0.07
100	0.5	0.10
100	0.6	0.10
100	0.7	0.09
100	0.8	0.08
100	0.9	0.06

95% CI calculated using the normal approximation

Date: 10 April 2019 Page 25 of 61

Assuming patients will use the OBI on average 3.5 times during a single chemotherapy course, 80 independent patients are estimated to receive a maximum of 280 OBI applications.

9.6 Data Management

As specified in Section 9.4 above, study data will be collected through two different sources:

- A respondent questionnaire developed to collect information from the primary person responsible for monitoring the OBI after application (ie, patients or, if appropriate, their caregivers). Responses will be collected either by paper or online.
- An eCRF for the HCP will be used to collect descriptive information about the HCP and the site, information about the time and date of OBI administration, and of events related to medication errors.

Upon inclusion of a new respondent **in**to the study (and after obtaining patient and respondent consent), the **HCP** will be asked to immediately complete information requested in the eCRF (ie, identification if the respondent is the patient or the caregiver, inclusion and exclusion criteria, and information of the current OBI application - medication errors and time and date of administration). The eCRF will subsequently generate a unique patient and respondent code (eg, UK-01-01-01). This code will be manually added to the ICF of the respondent by the **HCP** for reference purposes.

The HCP will give the respondent an envelope containing the instructions about how to complete the questionnaire (two options will be provided in the same envelope):

- a) Option 1. A document with the link to complete the questionnaire online.
- Option 2. Pre-paid and pre-filled envelope containing a paper copy of the respondent questionnaire and instructions for delivery to IQVIA to perform data entry.

The HCP will be subsequently responsible for conducting a telephone follow-up with the respondents to remind them about respondent questionnaire completion, within the timeframe established by the study protocol (ie, 27-72h post OBI application). For both options provided for questionnaire completion, the respondent will be initially requested to include the information on the respondent code (as provided by the HCP in the copy of the ICF, eg, UK-01-01-01), then respondent will be able to complete the rest of the questionnaire.

Date: 10 April 2019 Page 26 of 61

In case respondent completes the electronic questionnaire online, IQVIA will ensure that no contact information (eg, IP address, email, etc.) is recorded or captured in the corresponding database.

IQVIA will therefore generate and maintain two independent databases (one generated from the eCRF and one generated from the respondent questionnaire), with a unique identifier, but IQVIA will **not** hold information that can be used to identify or contact the respondent and clinical data, thus ensuring data privacy. Only the **HCP** will be able to identify the patient, through a patient tracking sheet, which will link the patient identity and the unique identifier. This document will be strictly maintained at the site.

eCRF

An eCRF (web-based form) will be used for collection of data reported by the **HCP**.

The eCRF will include specific logic checks and filters for collected variables in an effort to minimize errors in data entry. The eCRF will also allow the study team to obtain 'real-time' statistics on recruitment and eCRF completion progression.

Site staff will be trained on data entry and patient data will be handled in compliance with all applicable confidentiality and privacy laws within participating countries.

The use of a private login and password will be necessary to access the website functionalities.

Daily, weekly and monthly backups of data entered in the eCRF will be performed to prevent any data loss or damage.

The study database will be locked once validated. At database lock, edit access rights will be removed, in order to prevent any data modification. Read-only access will remain active.

The data collected through the eCRF will be stored for a minimum of 5 years on an IQVIA secure server.

Electronic respondent questionnaire

Data on the respondent questionnaire will be collected using an electronic data capture system (different to the eCRF) developed following a full validation process. A rigorous System Development Life Cycle (SDLC) is used for validation that complies with internal IT Standard Operating Procedures (SOPs) of the Primary Intelligence team of IQVIA. Unit testing and formal validation occur on all appropriate systems and components during the build stage. The SDLC is fortified with SOPs addressing validation for all

Date: 10 April 2019 Page 27 of 61

clinical and risk management-related applications. The internet-based repository will be used to store survey data and other relevant program information.

Questions are programmed to ensure that they are asked in the appropriate sequence. Skip patterns are clearly indicated. Respondents cannot go back to a question once the question has been answered and they cannot skip ahead. Response options presented in a list are randomized to minimise positional bias. Programming will be reviewed by Quality Control and simulated users (User Testing) prior to implementation.

Collected data will be entered and stored in a database specific to the survey.

Data will be checked in terms of consistency before data analysis:

Removal of duplicates (if required),

Product: Pegfilgrastim

- Data labelling and data formatting,
- Range and consistency checks for each variable to identify potential non admissible values,
- Cross-check the consistency of data for related variables (if feasible).

The study database will be locked once validated.

Participating respondents will access the website (https secured site) via a secure link unique to each respondent.

The data collected will be stored on a secure IQVIA server, and will be stored for a minimum of 5 years after the end of the study.

A data management plan (DMP) will be written to guide of all aspects of data handling. It will include all data forms and annotations, testing documentation and summaries, database documentation, merging of datasets and transfer of files into SAS for statistical analysis. All data collected during the study will be held confidentially.

As discussed in Section 10.3, the identities of patients and respondents taking part in the study will be controlled using unique identification codes. These source ID numbers will be held securely, and these data will be used solely for the purpose of identifying whether the respondent has completed the questionnaire.

Date: 10 April 2019 Page 28 of 61

9.6.1 Obtaining Data Files

Completed paper forms will be forwarded to IQVIA by respondents for data entry.

IQVIA data entry staff will enter the paper questionnaire into a database for analysis.

A database will be created and tested before data entry, two copies of the same database will be prepared for double data entry to be performed. Databases will be compared until no discrepancies are found. The final database will be merged with the online questionnaire results and transferred to SAS for analysis.

9.6.2 Linking Data Files

The only linkage required for the study will be between the data reported in the eCRF and that reported in the respondent questionnaire. Linkage will be performed using a unique code assigned to each patient and respondent (see Section 10.3). The same code will be used to collect all data related to OBI applications monitored by the same respondent, and each application will also be identified. The code corresponding to patient, respondent and administration will be electronically assigned at completion of the eCRF.

9.6.3 Review and Verification of Data Quality

This study is collecting data from patients or, if applicable, from caregivers through a questionnaire as the primary data source, and complementary data from the HCP through an eCRF. It is not planned to generate queries in the study and closed questions will limit the need for data checks.

9.7 Data Analysis

9.7.1 Planned Analyses

The statistical analysis will be conducted with SAS® statistical software or R. A detailed statistical analysis plan (SAP) will be prepared and accepted before the data analysis initiation.

All the respondents participating in the study who meet the eligibility criteria will be included in the sample of respondents in which reception of the PAC, awareness of key safety messages and behavioural intent to carry out recommended actions as described in the PAC will be assessed. Respondents monitoring more than one OBI application in the context of the study will complete reception of PAC, awareness of key safety messages and behavioural intent sections only for the first OBI application

Date: 10 April 2019 Page 29 of 61

All OBI applications reported by participant respondents will be included in the sample of treatments to estimate the proportion of OBI applications associated with medication error. OBI applications for Neulasta doses that have not been delivered (due to medication error) will be also included in the full analysis set of OBI applications. More than one OBI application can be reported for the same respondent.

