The source population will be the primary person responsible for monitoring the OBI after application, ie, patients or, if appropriate, their caregivers. This person will be defined as the "respondent". For every patient receiving OBI for Neulasta, the respondent will be defined at the time of study inclusion. Respondents can be included in the study multiple times at different chemotherapy cycles in which the OBI is being prescribed to the patient, if eligibility criteria including informed consent are met. In subsequent administrations of the questionnaire, data will only be collected to meet the secondary objective regarding medication errors (via a partial respondent questionnaire).

HCPs working at sites in which the OBI is being prescribed or expected to be prescribed will be approached for participation in the study.

Summary of Subject Eligibility Criteria

- Inclusion criteria
 - Respondent (ie, patients or caregivers primarily responsible for monitoring the OBI) who agrees to be contacted for the questionnaire.
 - Respondent aged 18 or more years.
 - Respondent with no cognitive impairment.
 - Respondent who can read and understand the language in which the study is being conducted and in which the PAC is provided.

Date: 10 April 2019 Page 12 of 61

Patient has been prescribed the OBI for Neulasta delivery for their current chemotherapy cycle.

Patient and respondent provide their written informed consent to participate in the study.

Exclusion criteria

Product: Pegfilgrastim

- Respondent personally works, or works on a consultancy basis, for any pharmaceutical company or advertising/research agency.
- Patient has participated or is participating in a clinical trial of Neulasta administered via OBI.

Follow-up

No follow-up is conducted after the questionnaire administration in this cross-sectional study.

Variables

- Respondent demographics and characteristics, including age, sex, educational level, self-reported language skills, self-reported confidence to monitor the OBI, health literacy - using the guestions from the Brief Health Literacy Screen (BHLS) questionnaire (Chew et al. 2004) -, respondent type (patient or caregiver)
- Respondent prior use and/or monitorisation of the Neulasta OBI
- Details of respondent receipt and use of the PAC
- Respondent reported awareness of key safety messages in the PAC
- Respondent reported behavioural intent to carry out recommended actions as described in the PAC

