- Device issues experienced by the patient (eg, whether the device came loose, red light came on, leakage, etc.) and any resulting actions
- Symptoms of adverse events experienced by the patient (eg, fever, chills, sweating, etc.) and related consultations with HCPs
- Details on dose delivery (eq. expected dose delivered on time, partial dose received, etc.)
- Occurrence of a replacement granulocyte colony stimulating factor (G-CSF) dose (eg, type of replacement and timing)

In addition, the HCP will report the following variables through an electronic case report form (eCRF), to be completed at the time of respondent identification and consent:

- HCP and site characteristics (only reported once per HCP)
- HCP awareness of methods to obtain the PAC

Date: 10 April 2019 Page 13 of 61

Date and time of OBI application

Device issues observed by the HCP at the time of OBI application (eg, the device coming loose, problems filling the device, leakage, etc.)

Study Sample Size

Product: Pegfilgrastim

This study aims to include approximately 80 respondents, however, the final sample size will ultimately depend on the uptake of the OBI in participating countries and willingness of respondents to participate. Expected OBI use in Europe is <10,000 patients per year, therefore, a sample size of 80 respondents is considered feasible.

Assuming patients will use the OBI on average 3.5 times during a single chemotherapy course, 80 independent patients are estimated to receive a maximum of 280 OBI applications.

Data Analysis

All the respondents participating in the study who meet the eligibility criteria will be included in the sample of respondents in which awareness of key safety messages and behavioural intent to carry out recommended actions as described in the PAC will be assessed. These outcomes will be assessed for the first monitored OBI application only.

Distribution of the PAC, awareness of key messages in the PAC and behavioural intent to carry out recommended actions as described in the PAC will be described at respondent level, providing the percentage of correct responses. A success measure will be used to define the success of the PAC.

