In case that for a unique patient, the respondent is different in subsequent administrations of the questionnaire (ie, from patient to caregiver, from caregiver to patient, or from caregiver to another caregiver), the new respondent would still be eligible if all eligibility criteria are met, but a full questionnaire would need to be filled in and he/she will be treated as a new respondent. The HCP will check at the time of study inclusion if the respondent identified has been included in a previous OBI administration, to avoid double counting of respondents.

Product: Pegfilgrastim

Date: 10 April 2019 Page 19 of 61

The number of potential respondents screened but not enrolled into the study will be recorded.

9.2 **Setting and Study Population**

The study is planned to be conducted in a number of EU countries in which the OBI is approved and utilized. A selection of EU countries are planning launching the OBI over the period of 2018 and 2019. Based on the current forecasted launch timetable, a preliminary selection of countries for this study is likely to include Germany,

Netherlands, Slovakia and/or UK. The final selection of countries will be informed by a country level feasibility assessment and will correspond to a combination of expected product uptake, adequate timing of the product launch and logistical barriers foreseen to allow for the completion of the study within the required timeframe, with a minimum of 2 different EU countries represented.

This rationale is based on factors that may change as the study progresses (ie, initial usage forecasts and planned launch schedule). Therefore, if recruitment of respondents is slower than anticipated other countries and/or sites may be added to meet sample size goals within the study timeline.

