9.3 Variables

Variables collected in the respondent questionnaire, to be administered approximately 27 to 72 hours after OBI application, will include:

- Respondent demographics and characteristics, including age, sex, educational level, self-reported language skills, self-reported confidence to monitor the OBI, health literacy - using the questions from the Brief Health Literacy Screen (BHLS) questionnaire (Chew et al. 2004) -, respondent type (patient or caregiver)
- Respondent prior use and/or monitorisation of the Neulasta OBI
- Details of respondent receipt and use of the PAC
- Respondent reported awareness of key safety messages in the PAC (eg, OBI alerts for Neulasta dose delivery or issues, time of removal of OBI, etc.)
- Respondent reported behavioural intent to carry out recommended actions as described in the PAC (eg, symptoms related to infection, issues with Neulasta dose delivery via the OBI, etc.)
- Device issues experienced by the patient (eg, whether the device came loose, red light came on, leakage, etc.) and any resulting actions*
- Symptoms of adverse events potentially related to medication errors experienced by the patient (eg, fever, chills, sweating, etc.) and related consultations with HCPs*
- Details on dose delivery (eg, expected dose delivered on time, partial dose received, etc.)*
- Occurrence of a replacement G-CSF dose (eg, type of replacement and timing)*

In addition, the HCP will report the following variables through an eCRF, to be completed at the time of respondent identification and consent:

- HCP and site characteristics (only reported once per HCP)
- HCP awareness of methods to obtain the PAC
- Date and time of OBI application
- Device issues observed by the HCP at the time of OBI application (eg, the device coming loose, problems filling the device, leakage, etc.)

^{*} Indicates variables to be collected in the partial respondent questionnaire

Date: 10 April 2019 Page 22 of 61

9.3.1 **Exposure Assessment**

Product: Pegfilgrastim

Patients included in the study will have been administered the OBI as per routine clinical practice.

9.3.2 **Outcome Assessment**

The primary endpoint for the respondent questionnaire is:

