9.7.2.3 Descriptive Analysis

9.7.2.3.1 Description of Study Enrollment

A description of the number and percentage of respondents and OBI applications will be reported:

- Study population: All respondents invited to participate in the study.
- Eligible set: All respondents included in the study population who fulfill all selection criteria. Detailed information about eligible criteria not fulfilled will be also reported.
- Enrolled set: All respondents included in the eligible set who accept to participate in the study or who sign the informed consent.
- Full analysis set of respondents: Will include all respondents enrolled in the study
 who complete the questionnaire corresponding to at least one OBI administration
 and have valid responses to allow for the assessment of the primary objective.
- Full analysis set of OBI administrations: Will include all OBI administrations
 monitored by respondents included in the full analysis set of respondents and for
 which the corresponding questionnaire is completed and allows for the
 assessment of the primary objective.

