9.9.3 Analysis Limitations

9.9.4 Limitations Due to Missing Data and/or Incomplete Data

Given the short time window in which the respondent needs to answer the questionnaire (27 to 72 hours after OBI application) there is an increased risk of non-response to the questionnaire, due to respondent lack of availability.

10. Protection of Human Subjects

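### A respondent who does not return the first full questionnaire has no route into the primary and PAC-receipt analyses, even if they return forms at later cycles

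*Protocol*

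**What the plan says.** **When the primary items are asked.** Section 9.7.1 has respondents who monitor several applications complete PAC receipt, "awareness of key safety messages and behavioural intent sections only for the first OBI application". The Abstract (Data Analysis) says of awareness and intent: "These outcomes will be assessed for the first monitored OBI application only".

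**What happens later.** The Abstract (Study Population) states: "In subsequent administrations of the questionnaire, data will only be collected to meet the secondary objective regarding medication errors (via a partial respondent questionnaire". Section 9.3 stars the items that go into the short form ("Indicates variables to be collected in the partial respondent questionnaire"). These are device issues, symptoms and related consultations, dose delivery and replacement dose. PAC receipt, awareness and intent are not starred.

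**Who gets another full form.** Section 9.1 requires one only when the respondent for a patient changes. For a returning respondent, the step described is: "The HCP will check at the time of study inclusion if the respondent identified has been included in a previous OBI administration". Its stated purpose is to avoid double counting.

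**Where the forms go.** Under section 9.6, completed questionnaires go to the CRO and the HCP completes an eCRF: "IQVIA will therefore generate and maintain two independent databases". The HCP makes a telephone reminder in the 27 to 72 hour window. Respondent codes may be used to identify whether a questionnaire has been completed.

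**Who is analysed.** Section 9.7.2.3.1 requires a completed questionnaire for at least one OBI administration and also valid responses for the primary objective. It limits the administration set to administrations "monitored by respondents included in the full analysis set of respondents". Section 9.7.2.2 rules out imputation.

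**Expected non-response.** Of the short window, section 9.9.4 says "there is an increased risk of non-response to the questionnaire".

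**The concern.** The trigger for the full form is the first application, not the first questionnaire received. A respondent whose first form never comes back is given the partial form at every later cycle and is never asked the primary questions again. That person may still be enrolled, seen at the site at each cycle and returning forms.

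The loss falls on the primary endpoint and on PAC receipt, in a study of about 80 respondents. The plan names the risk but offers no recovery beyond one reminder. A smaller sample widens the intervals that Table 1 compares with 70%. For an estimate below 70%, a wider interval reaches the threshold more readily.

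**Working it through.** **1. Does any rule let a first-form non-returner back in?**
- Section 9.7.1: the primary items are completed at the first in-study application only.
- Section 9.3: the partial form has no PAC-receipt, awareness or intent item.
- Section 9.1: a repeat full form is required only for a new respondent.
- Section 9.7.2.3.1: valid primary responses are needed. The allowance for at least one OBI administration does not help, because both conditions must hold and a later form contains no awareness or intent items.

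Reading the primary objective as section 8.1 defines it, no route remains for the same respondent.

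**2. Reproduce the plan's figures (section 9.5).** Table 2 uses half-width = 1.96 × √(p(1−p)/n).
- n = 80, p = 0.7: 1.96 × √(0.21/80) = 0.1004; the table has 0.10.
- n = 60, p = 0.7: 1.96 × √(0.21/60) = 0.1160; the table has 0.12.
- All 15 rows agree to two decimals, and 80 × 3.5 = 280 applications agrees. Neither figure is disputed.

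**3. Size of the loss.** Inputs are 80 enrolled (section 9.5) and a return rate r per application. The protocol gives no r, so 0.75 with a range of 0.60 to 0.90 is an assumption. The re-offer column also assumes that returns are independent between cycles and that every respondent has a second application.
- As written: 80r.
- One re-offer of the full form: 80(1 − (1−r)²).

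| r | As written | Half-width at 70% | One re-offer | Half-width at 70% |
|---|---|---|---|---|
| 0.60 | 48 | 0.130 | 67.2 | 0.110 |
| 0.75 | 60 | 0.116 | 75 | 0.104 |
| 0.90 | 72 | 0.106 | 79.2 | 0.101 |

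The half-widths apply to a proportion, such as PAC receipt or one question. The interval for the mean composite score depends on a standard deviation that the protocol does not give.

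**4. If non-return persists.** Let c be the chance that a first-cycle non-returner returns the re-offered form. The yield is 80(r + (1−r)c). At r = 0.75:
- c = 0.75 (independence): 75
- c = 0.40: 80 × (0.75 + 0.25 × 0.40) = 68
- c = 0: 60, so no gain

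The re-offer column in step 3 is therefore an upper figure for one re-offer if earlier non-returners are less likely to return.

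**5. The medication-error sample.** Section 9.7.1 and the Abstract include all OBI applications reported by participating respondents. Section 9.7.2.3.1 admits only administrations of respondents with valid primary-objective responses, and only where the form itself allows that objective to be assessed. Both rules cannot apply.

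**The case against.** **Three stronger readings are tempting, and the documents do not support them.**

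- *Missing the 72-hour window excludes the respondent.* The window is described as approximate, paper forms come by post, and no section rejects a late return. The loss follows only from never returning the first full form.
- *All later medication-error data are lost.* The data are still collected, and section 9.7.1 would count them. A loss limited to these respondents needs the primary objective in section 9.7.2.3.1 to mean awareness for respondents but something else for administrations. On that reading 80(1−r) × 2.5 × r gives 48, 37.5 and 18 returned reports at r = 0.60, 0.75 and 0.90. If the phrase means awareness at both levels, no partial form qualifies for anyone. If it follows sections 9.1 and 9.2.5, which attach the word primary to the medication-error objective, nothing is lost. No single figure can be attributed to the plan.
- *Awareness and PAC receipt are biased upward.* Section 9.9.4 attributes non-response to lack of availability, not low engagement. The direction is unknown.

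**The case for leaving the rule alone.** A fixed measurement point is simple, non-response is disclosed, and Table 2 already shows n = 60. At r = 0.75 the gain in half-width is only about 0.012. A non-returner may have read the first form, so a second offer mixes the card's effect with prior sight of the questions. Codes are already available to identify completion.

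**What stands.** The precision gain is modest and conditional, and prior sight of the form is a real cost that presentation by prior OBI use does not separate. But section 9.2.3.1 admits respondents with any number of earlier OBI uses, so the first in-study application is not a first-use measurement and the tie protects little. Completion can be tracked, but no step is described that passes it to the HCP who hands out the form.

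**Conclusion.** The point holds as a gap in a stated rule. A respondent who does not return the first full questionnaire has no way into the primary or PAC-receipt analyses, whatever they return later. Under assumed independent returns of 0.60 to 0.90, the yield from 80 enrolled is 48 to 72 as written, against at most about 67 to 79 with one re-offer. The benefit falls towards zero if the same people keep failing to return. No bias direction is established, and a late return is not itself an exclusion.

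The conflict between sections 9.7.1 and 9.7.2.3.1 over the medication-error sample is a separate matter. It needs reconciling whatever the return rate. The change should be made: the loss is avoidable and the correction is cheap.

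**What to change.** 1. In sections 9.1, 9.2.5 and 9.7.1, and the matching Abstract text, give the full questionnaire at each application until one full questionnaire has been received under that respondent code. Score the first one returned.
2. Use the existing respondent codes to pass a received or not-received status to the HCP, for example as a flag in the eCRF, so that the right form is handed out.
3. Report how many primary responses came from a later application, and give results for first-application responses alone alongside the full set.
4. Reconcile sections 9.7.1 and 9.7.2.3.1 so that the medication-error set does not depend on awareness responses. Correct the objective label in sections 9.1 and 9.2.5 to agree with section 8.2.

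**Cost.** Protocol wording and one status flag. Some respondents will be scored after more OBI experience or after seeing the unreturned form. The planned presentation by prior OBI use addresses the first; the first-application-only results address both.
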